Although clinical practice guideline applied in the routine treatment does not include meal-timing advices, but the importance of circadian rhythms in regulating mammalian physiological responses has been recognized (Mezitis and Bhatnagar, 2018). Mezitis and Bhatnagar, (2018) from United States of America (US) has emphasized the importance of circadian timing in people with diabetes because insulin sensitivity has been shown to exhibit circadian rhythmicity. Glycemic responses to meals are exaggerated in prediabetes and diabetes patients, more so when the meal is timed to be consumed out of sync with the metabolic pacemaker. Accordingly, Mezitis and Bhatnagar, (2018) have recognized optimal hormonal and hepatic function beginning in the early morning (4:00 a.m.) and fading in the early evening (4:00 p.m.). However, the times proposed by Mezitis and Bhatnagar, (2018) suitable for diabetes patients in US, and might not be able to apply in Malaysia diabetes management. This is because circadian timing system is affected by factors consisting of cosmic events related to the universe and earth, environmental factors (light, night and day duration, seasons) and lifestyles. To the best of our understanding, neither have there been any studies that have exploring the new concept of circadian timing in Malaysia prediabetes individuals, nor in Southeast Asia. The outcome of the present study will be able to recognize the optimal-meal-timing (chrono-nutrition) and activity/ sleeping (chrono-type) among Malaysian prediabetic individuals, in order to prevent prediabetes individuals from developing T2DM. Figure 1 shows the theoretical framework of the present study, adapted from Henry, Kaur and Quek, (2020). The theoretical framework shows that a schematic representation outlining the factors affecting the circadian clock system. Meal timing and dietary components (chrono-nutrition) play an important role in regulating circadian clocks, to enhance metabolic health and reduce the risk of type 2 diabetes. These recommendations could be considered as strategies to improve glycemic control, rather than focusing on the nutritional value of a meal alone, to optimize dietary patterns of diabetics. It is necessary to further elucidate this fascinating area of research to understand the circadian system and its implications on nutrition that may ultimately reduce the burden of type 2 diabetes.

[figure not shown]

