3. RESEARCH METHODOLOGY

Hypothesis:

The morning chronotype and early meal-timing are associated with low glycemic outcome among prediabetic individuals.

Research Questions:

Is the morning chronotype and early meal-timing are associated with better glucose tolerance among prediabetic individuals?

General objective:

To determine the associations of chronotype and chrononutrition with glucose tolerance among prediabetic individuals in Malaysia.

Specific objectives:

1. To examine the associations among chronotype, chrononutrition and glucose outcomes.
2. To investigate the association between lifestyle factors (physical activity level, light exposure, diet timing, sleep pattern) and chrononutrition.
3. To investigate the association between anthropometry measurements and glycemic outcomes.

Description of Methodology:

Participants will be recruited using the convenience sampling method. The proposed study will be conducted in community clinics in Malacca, Malaysia. Malacca is the capital of the coastal state, located in southwestern Malaysia, with an estimated total population of 0.93 million in the year 2019 (Department of Survey and Mapping Malaysia, 2021). In 2019, National Health and Morbidity Survey reported that 17% of Malaccan adults had hyperglycemia and 13.7% of them had known diabetes. Malacca is 1 out of the top five states showing the highest prevalence of diabetes in Malaysia (IPH, NIH and MOH, 2019). Permission to carry out data collection has been granted by the Medical Research and Ethics Committee (MREC) (RSCH ID-21-00114-IVI). The study protocol has been reviewed and approved by the Tunku Abdul Rahman University College (TARUC) research ethics committee (TAR UC/EC/2021/02-3).

During the process of recruitment, a trained research assistant (one of the co-researcher), clinical dietitian (one of the co-researcher) or family medicine specialist

(one of the co-researcher) will inform potential prediabetic individuals research protocol verbally and written information will be provided. Newly diagnosed prediabetic individuals who are agreeable to participate will provide written informed consent. Baseline and follow up appointments will be determined based on the community clinic appointment schedules. Those who decline to participate will continue to receive their routine treatment as usual, and care provided to each prediabetic individual will not be affected by the decision to either participate or not participate in the study.

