pattern from the validated questionnaires PSIQ and light exposure from the validated questionnaire HLEQ.

Statistical Analysis

All data will be performed statistical analysis using the SPSS software version 20 (SPSS Inc., Chicago, IL, USA). The socio-demographic will be presented as mean, standard deviations, median, interquartile range, frequency, and percentage. Data cleaning will be performed to exclude the outlier data before the normality is checked using Kolmogorov-Smirnov Test. The investigator considered $p < 0.05$ to be statistically significant. Chronotype, sleep quality, and light exposure will be analyzed as categorical variables whereas dietary intake, chrononutrition, anthropometry, glycemic measure, and physical activity will be analyzed as continuous variables.

The investigator will perform a multivariable generalized linear model to examine the association between night meal pattern (last night mealtime either dinner or supper with calories intake, frequency of night snacking, and the total number of the night snacking) and glycemic outcome (HbA1c, FPG, 2hPPG, CGM profile) by adjusting for the potential covariates. Specifically, nighttime will be characterized by the time range from 1900 and 0659 hours based on Malaysia solar time. The investigator will explore the late-night meal timing in 2000, 2100, and 2200 to examine its association with glycemic outcomes. The potential confounders include sociodemographic characteristics, physical activity, sleep pattern, sedentary behavior, diet quality, and light exposure will be controlled. ANCOVA test will be performed to understand the association between chrononutrition (breakfast skipping, meal frequency, eating window, sleep timing, chronotype, and fasting pattern) with glycemic variables, controlling for potential covariates (sociodemographic characteristics, light exposure, diet quality, physical activity and sleep pattern).

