To investigate the association of physical activity (MET score and steps count), sedentary behaviors (MET score), sleep pattern (sleep duration), diet quality (distribution of total energy, carbohydrate, protein, and fat), and light exposure (timing responded to a different type of light) with glycemic outcome, the multivariable generalized linear model will be conducted. Meanwhile, anthropometric measures (body mass index, body fat, and waist circumference) will be categorized as either normal or overweight and obesity group, followed by using logistic regression to examine the association between anthropometry status and glycemic outcome (non-diabetes or diabetes). In addition, the glycemic outcome will be categorized into diabetes incidence (diabetes and non-diabetes) to determine the participants who had been diagnosed with diabetes at 6 months. A logistic regression test will be used to examine the association between early and late-night mealtime and diabetes incidence.

Quality control

To ensure that the database accurately reflects the data reported in the questionnaires, a pre-test will be carried out. The research assistant trained to conduct the study procedures included interviewing administrative questionnaires, CGMS device, 3 days dietary record, and pedometer. Monthly meetings are held with the principal

investigator to review study procedures and progression. A monthly report will be documented after the meeting.

Data monitoring and management

Participants are anonymized and assigned with a specific ID at study entry. To ensure accuracy and completeness of data entry, data are checked by identifying if there is any outlier or missing value. The data checking process is performed in the first, third and sixth month of the data collection, such that the experience gained can be used to train the research assistant for improvement. Paper documents are kept in a locked cabinet and electronic data are stored on password-protected computers which can only be accessed by research team members. All records will be kept for at least 5 years after completing the study. After 5 years, all papers will be shredded using an office shredder. Extra care should be taken with sensitive or confidential information and a secure paper destruction service bin used. Digital data will be destroyed by deleting or overwriting information and destroying the physical media, such as CD rom.

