APPENDIX I**Chrononutrition Profile Questionnaire**

364

365

366

367

Project Name:

Meal Timing and Glucose Tolerance

Date of interview:

		/				/				
d	d		m	m	m		y	y	y	y

368

369

370

Chrononutrition Profile – Questionnaire (CP-Q)

371

372 Directions: The following questions are designed to assess the general timing of your eating.
 373 Please choose the one response that best fits your typical behavior and preferences.
 374 The term “eating event” refers to any time you eat something that contains calories. For
 375 example, this could be a meal, a snack, or a drink.

376

If you were entirely free to plan your day,

377

378 A1. What time would you prefer to wake up?

379 Please indicate A.M. or P.M. as part of your response.

380 _____ A.M./P.M.

381

382 A2. How soon after waking up would you prefer to have your first eating event of the day?

383 _____ hours _____ minutes

384

385 A3. How soon before bed would you prefer to stop eating?

386 _____ hours _____ minutes

387

388 A4. What time would you prefer to fall asleep? Please indicate A.M. or P.M. as part of your
 389 response. _____ A.M./P.M.

390

391 B1. On average, in a typical week (a 7-day period), B1. How often do you eat breakfast?

392 _____ 0 days _____ 1 day _____ 2 days _____ 3 days _____ 4 days _____ 5 days
 393 _____ 6 days _____ 7 days

394

395 B2. What is your largest meal of the day?

396 _____ Breakfast _____ Lunch _____ Dinner/Supper

397 _____ Other meal (Please describe: _____)

398

399 B3. How often do you eat a snack after your last meal of the day?

400 _____ 0 days _____ 1 day _____ 2 days _____ 3 days _____ 4 days _____ 5 days _____ 6
 401 days _____ 7 days

402

403 B4. How often do you wake up in the night to eat?

404 _____ 0 days _____ 1 day _____ 2 days _____ 3 days _____ 4 days _____ 5 days _____ 6
 405 days _____ 7 day

406

On average, on a typical workday or school day,

407

408 C1. What time do you wake up?

409 Please indicate A.M./P.M. as part of your response.

410

411 _____ A.M./P.M.

412

415
416 C2. What time is your first eating event of the day?
417 Please indicate A.M./P.M. as part of your response.
418 _____ A.M./P.M.
419
420 C3. What time do you eat lunch?
421 Please indicate A.M./P.M. as part of your response.

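### The plan promises an optimal meal time, but its specified glycaemia models use eating clock time only for the last night meal; first-meal and daytime times are collected and not named as timed exposures

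*Combined protocol and SAP*

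**What the plan says.** **The promise.** Section 1 (Introduction and Justification) cites a US-based window of best metabolic function from 04:00 to 16:00, doubts that it carries over to Malaysia, and states: "The outcome of the present study will be able to recognize the optimal-meal-timing (chrono-nutrition) and activity/ sleeping (chrono-type) among Malaysian prediabetic individuals". The end of Section 1 and the summary that closes the literature review (4.0) repeat the promise and point to national policy and guidelines.

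**The hypothesis** (Section 3): "The morning chronotype and early meal-timing are associated with low glycemic outcome among prediabetic individuals". The protocol does not say which meal, or what clock time, counts as early.

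**The models** (Section 3, Statistical Analysis):
- A generalized linear model of night meal pattern, namely "last night mealtime either dinner or supper with calories intake, frequency of night snacking, and the total number of the night snacking", with night defined as 19:00 to 06:59. It adds: "The investigator will explore the late-night meal timing in 2000, 2100, and 2200 to examine its association with glycemic outcomes".
- An ANCOVA whose exposures are "breakfast skipping, meal frequency, eating window, sleep timing, chronotype, and fasting pattern".
- A lifestyle model that includes the distribution of energy and macronutrients, labelled as diet quality.
- For diabetes at 6 months: "A logistic regression test will be used to examine the association between early and late-night mealtime and diabetes incidence".

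**The data.** The Chrononutrition Profile Questionnaire (CPQ, Appendix I) asks "C2. What time is your first eating event of the day", and asks for lunch time (C3) and last eating event (C4), with D2 to D4 for free days. The exposure-measures text in Section 3 derives energy and macronutrients in five clock periods and by hour. The CGM text says those data will be used to obtain the optimal meal timing and will be matched with the food diary.

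**The concern.** The deliverable is a best time to eat across the day. The analysis looks at clock time only at the end of the day. Three late-evening cut-points say nothing about breakfast or lunch, and cannot examine the 04:00 to 16:00 window that the introduction sets out to revisit.

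As specified, the person-level models can say whether a later last meal goes with worse glycaemia. They cannot say whether starting to eat earlier matters, or where an optimum lies. A statement about optimal meal timing would then rest either on late-evening contrasts alone or on a timing variable chosen after the data were seen. The findings are offered as input to policy and clinical guidelines, so that gap matters.

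**Working it through.** **1. Collected timing variables against named exposures**

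| Timing information | Source | Exposure in a specified glycaemia model? |
|---|---|---|
| Last night mealtime | CPQ C4/D4, diary | Yes: generalized linear model (20:00, 21:00, 22:00) and logistic regression |
| Night snacking | Diary, questionnaire | Yes, as frequency and number within the night period |
| First eating event | CPQ C2/D2, diary | Not named |
| Lunch time | CPQ C3/D3, diary | Not named |
| Energy in five clock periods and by hour | Diary, second day | Not named; the energy distribution in the lifestyle model is not said to be by time of day |
| Eating window, fasting pattern, breakfast skipping | CPQ, diary | Yes (ANCOVA), but not as clock times |
| CGM matched to diary | CGM text, Section 3 | Purpose stated; no model, estimand or criterion |

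**2. How far eating window stands in for first-meal time**

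The plan does not define eating window; take it as last minus first meal. With correlation ρ between first and last mealtime, and s = SD(last)/SD(first),

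corr(window, first) = (ρs − 1) / √(1 + s² − 2ρs).

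The values of ρ and s are assumptions:
- ρ = 0, s = 1: −0.71, so 50% of first-meal variance is shared.
- ρ = 0.5, s = 1: −0.50, so 25%.
- ρ = 0.5, s = 1.5: −0.19, so 4%.
- ρ = 0.7, s = 1.5: 0.05, so about 0%.

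The range is 0% to 50%. If all meals move earlier together, the window does not change. Window and last mealtime together would fix first-meal time, but the plan puts them in different analyses.

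**3. The plan's own sample size**

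Inputs from the sample size calculation: effect size 0.13, two-sided α = 0.05, power 0.90, single regression coefficient. Reading 0.13 as f² and using a noncentral t distribution with δ = √(f²N) and df = N − 2:
- N = 82 gives power 0.897.
- N = 83 gives δ = √(0.13 × 83) = 3.285 and power 0.901.

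So 83 reproduces, as does 83/(1 − 0.5) = 166. The protocol labels 0.13 a β-coefficient, but only the f² reading gives 83. That is a separate matter.

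**4. Illustration: power if the association lies with first-meal time**

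Partial r = √(0.13/1.13) = 0.339. If last mealtime is related to glycaemia only through its correlation c with first-meal time, then r′ = 0.339c and f²′ = r′²/(1 − r′²). At N = 83:

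| c (assumed) | r′ | f²′ | Power of last-mealtime test |
|---|---|---|---|
| 0.2 | 0.068 | 0.0046 | 0.094 |
| 0.3 | 0.102 | 0.0105 | 0.151 |
| 0.5 | 0.170 | 0.0296 | 0.341 |

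Modelling first-meal time itself would give 0.90.

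**5. Illustration: an optimum inside the observed range**

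With a quadratic truth at the same R² (0.13/1.13 = 0.115), simulation gives a straight-line test power of 0.10 (optimum at the mean) to 0.43 (optimum 0.5 SD away). A 2-df curve has about 0.77. The plan does not state a straight-line test, so these are not the power of the planned analysis.

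**6. Checks on the remedy**
- A 2-df test when the truth is linear: noncentral F with λ = 0.13 × 83 = 10.79 and df 2, 80 gives power 0.83, against 0.90 for the linear term.
- Simulated null data, n = 83, normal exposure, 3-knot restricted cubic spline: about 35% of fits show a minimum inside the data. Also requiring a significant nonlinear term cuts this to about 2.5%.

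**The case against.** The strongest opposing case is that the plan does test early against late eating. The hypothesis does not tie early to the first or a daytime meal. The cohort study that supplies the effect size concerns late dinner. Last mealtime is examined by generalized linear model and by logistic regression, and chronotype is in the ANCOVA. All of this stands. A reader might infer that the early-timing hypothesis cannot be tested at all; the documents do not support that.

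Second, a reader might infer that first-meal timing is wholly absent. It is not: eating window, fasting pattern and breakfast skipping carry some of it. But they are indirect, as step 2 shows. Two people eating 07:00 to 19:00 and 11:00 to 23:00 share a 12-hour window. The last-mealtime model separates them, but cannot say whether the start or the end of eating matters.

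Third, the CGM and diary matching is stated as the route to an optimum, so the intention exists. The defect there is missing specification. Likewise, the energy distribution in the lifestyle model might be meant by time of day; the text leaves this open.

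Fourth, the formal objectives speak of associations, and the optimal-timing statements sit in background text. That supports rewording as an acceptable remedy. It does not remove the mismatch.

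Finally, the power figures in steps 4 and 5 rest on assumed values and ignore the ANCOVA proxies. They illustrate a cost and do not establish the point.

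**Conclusion.** The point holds in a limited form. The specified person-level models test eating clock time directly only for the last night meal, and none can locate an optimum across the day. First-meal and daytime times are collected but not named as timed exposures, and the CGM-diary analysis has no model or criterion.

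This follows from comparing the listed exposures with the collected variables and needs no numerical assumption. The size of the loss cannot be fixed from the documents. Power of 0.09 to 0.34 is an illustration that depends on an assumed first-to-last correlation of 0.2 to 0.5, on 0.13 being f², and on the association lying wholly with first-meal time. The point does not invalidate the late-night analyses. It is a cheap improvement, worth making before analysis.

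**What to change.** In the Statistical Analysis section:

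1. Add time of first eating event (CPQ C2/D2), continuous, as a labelled secondary exposure in the same covariate-adjusted generalized linear model.
2. Fit eating midpoint (C2/C4, D2/D4) and the energy shares in the five clock periods in separate models. Midpoint is the average of first and last mealtime, so the three must never enter together. The shares sum to the whole day, so all five cannot enter together either. Using the protocol's own periods avoids borrowing the 16:00 limit that the introduction doubts.
3. For each, report the linear term first, then a 3-knot restricted cubic spline.
4. Claim an optimal meal time only if the nonlinear term is significant, the fitted curve has an interior minimum, and a confidence interval for its location is given.
5. Otherwise, reword the optimal-timing statements in Section 1 and in the literature summary (4.0) to say that the study examines associations of meal timing, chiefly late-night timing, with glycaemia.

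**Cost.** Plan wording and a few extra models; no new data. There are more secondary tests, and the 2-df test has power 0.83 rather than 0.90 if the truth is linear, which is why the linear term comes first. If two, three or four clock-time terms had to share α by Bonferroni (10 predictors assumed, f² = 0.13), power at 83 would be 0.84, 0.80 or 0.76, so they should stay labelled as secondary. The energy shares rest on one diary day, because the plan analyses the second day only.

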Study outcomes	
The main outcomes of this study are
 
 1) The change of baseline glycated hemoglobin (HbA1c) among prediabetes adults at 6 months. 2) The change of baseline fasting plasma glucose (FPG) among prediabetes adults at 6 months. 3) The change of baseline 2-hour post-load plasma glucose among prediabetes adults at 6 months. 4) The change of baseline continuous glucose monitoring (CGM) profile among prediabetes adults at 6 months. 
Secondary outcome of this study are
 
 1) The change of eating misalignment among prediabetes adults at 6 months. 2) The change of chronotype among prediabetes adults at 6 months.
Sample Size	120 prediabetic individuals
Study Duration	1 March 2022 until 31 December 2023
Name and Address of Sponsor	Fundamental Research Grant Scheme (FRGS), Ministry of Higher Education/ UMalaya (FRGS/1/2021/SKK06/TARUC/02/1)

Ethics Approval	Tunku Abdul Rahman University Management and Technology Ethics Committee (TAR UC/EC/2021/02-3) Medical Research and Ethics Committee (RSCH ID-21-00114-IVI)
-----------------	---

Executive Summary:

Early meal timing affects the circadian rhythmicity and influenced the postprandial blood glucose level in response to meal in diabetes patients. In the other words, diabetes patients with earlier meal timing had a stable glycemic control compared with those with late meal timing. This is a new concept to switch the meal timing earlier than later in diabetes self-monitoring management. However, there is insufficient evidence from Southeast Asia to determine the optimal-meal-timing and its association with glycemic measures in prediabetes individuals. Hence, this study carried out to determine the associations of chronotype and chrononutrition with glucose tolerance among prediabetic individuals in Malaysia.

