In Malaysia, there are no specific guideline for prediabetes individual and they are managed according to the latest Clinical Practice Guideline in Malaysia (MOH *et al.*, 2020). For prevention prediabetes to further develop to diabetes, lifestyle intervention such as weight loss (5-10% of initial body weight), regular physical activity (150 min/week), with dietary strategies including reduced calories and behavior modification are recommended in Clinical Practice Guideline in Malaysia (MOH *et al.*, 2020). A high fibre diet (20-30g/day with 5 to 7 servings/day) consisting of vegetables, fruits, legumes and whole grains is encouraged too (MDES, 2020). All the prediabetic individuals will be referred to dietitian and nurse educators for 6 months routine treatment, prior to T2DM diagnosis, determined by second-round of oral glucose tolerance test (OGTT) in 6-month period (MOH *et al.*, 2020). To the puzzlement of many diabetes researchers and clinicians, some of the prediabetes cases showed tremendous improvement in their blood sugar result, yet some of the prediabetes

individuals developed full-blown of T2DM with their blood sugar result higher than the normal range; despite all of them followed the same routine treatment from healthcare clinics. Perhaps, besides the usual routine treatment from Clinical Practice Guideline (MOH *et al.*, 2020) (weight management, physical activity advices and dietary modification); prediabetic individuals who able to improve their blood sugar result in 6-month period has particular meal-timing, compared to those has uncontrolled blood sugar result in 6-month period.

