Identifying novel, potentially modifiable, life-style factors associated with increased blood sugar level, can lead to innovative strategies for improving health status and preventing T2DM in prediabetes individuals. The proposed study presents a novel approach as a paradigm shift in Malaysia diabetes management. The investigator anticipate that this study will not only reveal the optimal-meal timing (chrono-nutrition) for prediabetic individuals, it will also disclose the associations of chrono-nutrition with glycemic measures and anthropometric measurements in prediabetic individuals. The findings may act as guidance to government bodies to develop policies at national level. For non-governmental agencies, the outcome may be applied to plan public campaigns to improve blood sugar outcome in prediabetic and diabetic individuals. Besides, optimal-meal timing and factors associated with chrono-nutrition would be identified and management of these factors can be delivered to diabetic individuals. For example, improvement of the dietary pattern and timing coupled with physical activity to ensure good blood sugar control. Understanding the optimal-meal-timing for blood sugar control could tailor education and intervention in diabetes management. This research has potential to be converted into a larger cohort study and intervention whereby prediabetic individuals could be follow-up for longer duration to study health outcomes and blood sugar control to manage the diabetes

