Anthropometric measurements (Appendix J) will be measured at the first, second and third visit. Body weight, body fat percentage and visceral fat of each participant will be measured twice using a body fat analyzer (HBF-375, Karada) and recorded to the nearest 0.1 kg, 0.1 % and 1 unit, respectively. Participants will be weighted with their minimal cloths on, barefoot, without belt and emptied pockets. They will be asked to stand still with the body weight equally distributed on both feet. Participants have to be in the Frankfurt plane, where the body is upright, upper limbs are at the body's sides with the palms facing forward, feet flat and directed forward, directly facing the researcher assistant. The height of each participant will be measured twice using a SECA portable stadiometer Model 217 (SECA GmbH & Co., Hamburg, Germany) attached to a smooth wall and recorded to the nearest 0.1 cm. Participants will be asked to stand erect, in their bare feet, with their heels, buttocks, head and shoulder blades in a vertical line against the wall. Height will be measured in the upright position against a vertical scare and with the head positioned so that the top of the external auditory meatus is in the level with the inferior margin of the bone orbit. Waist and hip circumferences of the respondents will be measured twice, according to the standardized protocol by the WHO (2008). Waist circumference will be measured at the approximate midpoint between the lower margin of the last palpable rib and the top of the iliac crest. Hip circumference will be measured around the widest portion of the buttocks, with the tape parallel to the floor. For both measurements, the participants should stand with feet close together, arms at the side and body weight evenly distributed, and should wear little clothing. Both waist and hip circumferences will be measured to the nearest 0.1 cm by using a Lufkin tape model W606PM (Apex Tool Group, Sparks, MD, USA). The reported measurements are the average values from both readings.

Study Outcomes

The main outcome of the study is the glycemic outcome including FPG (mmol/L), 2hPPG (mmol/L), HbA1c (%), and glucose variability from CGMS. The secondary outcomes are chronotype from the validated questionnaire MCTQ, and chrononutrition from the validated questionnaire CPQ, 3 days dietary record, anthropometry measurements, physical activity level from the validated questionnaire IPAQ, sleep

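### No planned model relates meal timing or chronotype to anthropometry, and the late-meal glycaemia models name no weight or adiposity covariate

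*Combined protocol and SAP*

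**What the plan says.** **Anthropometry as a result.** The Introduction and Justification expects of the study that "it will also disclose the associations of chrono-nutrition with glycemic measures and anthropometric measurements in prediabetic individuals". Study Outcomes (Research Methodology) states: "The secondary outcomes are chronotype from the validated questionnaire MCTQ, and chrononutrition from the validated questionnaire CPQ, 3 days dietary record, anthropometry measurements". Body weight, body fat, waist and hip are measured at all three visits, according to the anthropometry paragraph.

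**Anthropometry in other places.** Specific objective 3 in Research Methodology reads "To investigate the association between anthropometry measurements and glycemic outcomes", and objective 3 in the synopsis is to the same effect. The summary closing the Literature Reviews (4.0) also treats anthropometry as something related to glycaemia. The synopsis gives two secondary outcomes, the first being "The change of eating misalignment among prediabetes adults at 6 months" and the second change in chronotype; anthropometry is not among them.

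**The models (Statistical Analysis).** The night-meal generalized linear model, the chrononutrition ANCOVA and the lifestyle model all have glycaemic outcomes. The covariate lists of the first two cover sociodemographics, activity, sleep, diet quality and light exposure, and the night-meal list adds sedentary behaviour. Neither names weight, BMI, waist or body fat. The logistic model of mealtime and diabetes incidence names no covariates. Anthropometry enters one analysis, a "logistic regression to examine the association between anthropometry status and glycemic outcome (non-diabetes or diabetes"), with the measures split into normal versus overweight or obese.

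**Routine care.** The Introduction describes guideline care as a "lifestyle intervention such as weight loss (5-10% of initial body weight") together with activity and dietary advice. It then asks whether people who improve over six months under that care differ in meal timing.

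**The concern.** There are two linked gaps.

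First, a result that the Introduction anticipates, on a variable that Study Outcomes calls an outcome, has no analysis behind it.

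Second, the study's motivating question is whether meal timing adds something beyond weight management, activity advice and diet. Two of those three elements are represented among the covariates and weight is not. Participants who start heavier, or who lose less weight, may also eat later. If so, a late-meal coefficient for HbA1c, fasting glucose or 2-hour glucose mixes timing with adiposity, and no planned output would show how much. The protocol hopes its findings will inform national guidance on meal timing, so a reader will want to know this.

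**Working it through.** **1. Does any model fill the gap?** The planned analyses, side by side:

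- Night-meal generalized linear model: glycaemic outcome; no anthropometric term named.
- Chrononutrition ANCOVA (includes chronotype): glycaemic outcome; no anthropometric term named.
- Lifestyle generalized linear model: glycaemic outcome; no anthropometric exposure named.
- Anthropometry logistic model: dichotomised anthropometry and diabetes status; no meal-timing or chronotype term and no change score. The gap remains whichever variable is taken as dependent.
- Mealtime logistic model: diabetes incidence; no covariates named.

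None relates meal timing or chronotype to anthropometry, and none of the late-meal models names adiposity or its change.

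**2. Reproduce the plan's sample size.** Inputs from Sample size Calculation: t test of a single coefficient in multiple regression, two-sided alpha 0.05, power 0.90, effect size 0.13 (labelled a beta-coefficient), dropout 50%. With noncentrality sqrt(f² × N) and N − k − 1 degrees of freedom for k predictors, entering 0.13 as f² gives N = 83 (power 0.901 at k = 1). Then 83/(1 − 0.5) = 166. Both figures reproduce. If 0.13 were a standardised beta, f² would be 0.13²/(1 − 0.13²) = 0.0172 and about 614 would be needed. The reading consistent with 83 is therefore f² = 0.13. With one predictor it implies a standardised slope of sqrt(0.13/1.13) = 0.34.

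**3. Size of the omission.** The documents give no correlations, so these are assumptions. Let r be the correlation of mealtime with weight change and g that of weight change with HbA1c change, with no direct timing effect. The slope shown by a model without weight change is r × g:

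- Low end: 0.1 × 0.3 = 0.03, and 0.03/0.34 = 9%.
- High end: 0.3 × 0.5 = 0.15, and 0.15/0.34 = 44%.

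**4. Chance of a significant late-meal result from this alone.** Using f² = b²/(1 − b²) with b = r × g and the power formula above, the probability at N = 83 runs from 0.058 (b = 0.03) to 0.277 (b = 0.15), against a nominal 0.05. At r = 0.3, g = 0.4 (b = 0.12) it is 0.19 at N = 83, 0.26 at the synopsis N of 120 and 0.34 at N = 166.

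Steps 3 and 4 ignore the planned adjustment for activity and diet, which would probably absorb part of the effect.

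**5. Precision cost of adding weight change.** Keep f² = 0.13, multiply it by (1 − r²) and set k = 2. N for 90% power is 84, 87 and 91 at r = 0.1, 0.2 and 0.3. Power at N = 83 is 0.898, 0.889 and 0.872.

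**The case against.** The case against has real force.

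- **The anticipated result is not an objective.** It is one sentence in the Introduction. Both versions of objective 3 and the literature summary relate anthropometry to glycaemia, and the plan delivers that analysis. The Study Outcomes list also labels activity, sleep and light exposure as secondary outcomes although the models use them as exposures or covariates, so loose labelling is a fair explanation. This stands. It makes the first gap a matter of reconciling sections as much as adding models.
- **The link from care to timing is assumed.** The Introduction says routine care contains no meal-timing advice, and people previously exposed to such information are excluded. Nothing in the documents shows that those who lose weight also eat earlier. This stands, and the correlations above are therefore labelled as assumptions.
- **Weight change may be a mediator.** The literature review itself describes mistimed eating leading to weight gain in animals. Omitting a mediator is correct for a total association. This also stands, and it limits what a weight-change model can show. It does not apply to baseline BMI, which precedes follow-up.
- **Diet and activity are already adjusted for.** They capture weight only indirectly, and although the confounder wording is open-ended, it does not commit to weight.

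A reader might infer three stronger things that the documents do not support:

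- That the 50% allowance shows unequal uptake of weight-loss care. It inflates the sample for non-response and non-compliance in follow-up and says nothing about adherence to care.
- That the induced slope could exceed the planned effect, by setting 0.15 against 0.13. That reads 0.13 as a standardised beta, which its label suggests but N = 83 contradicts.
- That the study asserts timing matters instead of diet. The Introduction offers that idea only as a possibility.

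**Conclusion.** The point holds as a gap in the analysis plan. No planned model relates anthropometry to meal timing or chronotype, and the two main chrononutrition models leave out adiposity although weight management is part of the care they are meant to look beyond. A late-meal association may partly reflect baseline adiposity or differing weight loss. On the assumed correlations the induced slope is 0.03-0.15, or 9%-44% of the slope of 0.34 that the calculation is powered for, before any reduction from adjusting for activity and diet.

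It would go too far to say that timing and weight loss cannot be separated. The models as written do not examine it, but the measurements allow it to be examined. Nor should a weight-adjusted coefficient decide the conclusion, since conditioning on a possible mediator does not isolate a timing effect. This is an inexpensive improvement that should be made; it does not invalidate the planned association analysis.

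**What to change.** 1. Reconcile the Introduction, Study Outcomes, synopsis, both objective lists and the literature summary on whether anthropometry is an outcome, a predictor of glycaemia, or both.
2. Add baseline BMI (or weight) to the covariate lists of the night-meal model and the chrononutrition ANCOVA.
3. Add linear models of six-month weight, waist circumference and body-fat percentage on last mealtime and chronotype, adjusted for the baseline value and the same covariates. Label them secondary or exploratory.
4. Beside the night-meal models for HbA1c, fasting glucose and 2-hour glucose, show a version that adds six-month weight change, labelled supplementary and descriptive. The model without weight change remains the main total-association result.

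The cost is SAP wording and a few models on measurements already scheduled at every visit. For assumed r up to 0.3, adding weight change costs the equivalent of at most 8 evaluable participants (91 − 83). The downsides are a few more secondary tests, which the exploratory label should make plain, and the risk that readers over-interpret the supplementary model. One sentence in the SAP on possible mediation would address that risk.
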